#### **Indication for transfusion**

- Hb <7.0 mg/dl
- Anemic symptoms developed:
  - A decrease in blood pressure to <100 mmHg systolic,

- [tachycardia](#) greater than 100 beats/min
- Orthostatic hypotension , lightheadedness, Chest pain/palpitation, confusion (due to a low bp)
- Low urine output of <30 ml/h, after initial fluid challenge with 500 ml normal saline in patients with a hemoglobin level between 7.0 and 8.0 mg/dl.

## Calculations and measurement of blood loss

Visible blood loss = intraoperative blood loss + postoperative drainage amount; intraoperative blood loss = weight of liquid in the suction bottle – weight of intraoperative rinsing fluid + increased weight of intraoperative gauges and towers.

Hidden blood loss is calculated based on the linear equations provided by Gross. The formula is as follows:

1)Hidden blood loss = total blood loss before and after surgery – visible blood loss.

2)Total blood loss before and after surgery = preoperative blood volume × (HCT difference before and after surgery/mean HCT before and after surgery).

3)Preoperative blood volume = K1 × height (m) + K2 × body weight (kg) + K3, where K1 = 0.3669, K2 = 0.0322, and K3 = 0.6041 in male patients, and K1 = 0.3561, K2 = 0.0331, and K3 = 0.1833 in female patients.

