**Primary Hypothesis:**

TXA reduces intraoperative and postoperative (up to 7 days) blood loss and transfusion requirements.

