**Exclusion:**

- 1) ASIA class V
- 2) Patient unable to consent
- 3) Patient with chronic kidney disease stage III or above: baseline plasma creatinine>1.5mg/dL
- 4) Patient with known liver failure
- 5) Patients on anticoagulation or dual antiplatelets (presence of vascular stents).
- 6) Patients with artificial valves.
- 7) Patients with allergy to TXA
- 8) Patients with platelet count < 150 000
- 9) Patients with PT>15s
- 10) Patients with APPT>38s
- 11) History of stroke or (an) unprovoked thromboembolic event(s).
- 12) History of intracranial bleeding,
- 13) Pregnancy
- 14) known defective color vision
- 15) history of venous or arterial thromboembolism or active thromboembolic disease
- 16) Patients with severe pulmonary or cardiac disease.
- 17) Patients who refuse transfusion of blood products
- 18) Patients with chronic anemia with Hg<8
- 19) Patients undergoing lumbar fusion for disease other than DDD (neoplasm)
- 20) Patients undergoing lumbar fusion by anterior or lateral approach.
- 21) Minimally invasive TLIF are excluded.
- 22) Emergent cases.
- 23) Women on hormonal contraception
- 24) Retinal vein or artery occlusion
- 25) Hypercoagulability
- 26) Seizure disorder
- 27) Current use of tretinoin
- 28) Current use of chlorpromazine
- 29) Breast feeding

Variables	Preop	Hospitalization	6-week f/u	3-month f/u
Demographics	X			
BHCG				
LFT *	X			
Coags (PTT/PT/INR)	X			
GFR	X	POD1		
SF Rand/ PROMIS	X		X	X
CBC	X	X		
Complications (DVT,PE,SSI,TE)		X	X	
Visual testing *	X	POD1		
New deficit		POD1		
	X	Intraop 1h postop (PACU) POD1,2,3		
Drain output/duration		X		
Blood Loss		X		
3D-CAM/CAM ICU*	X	X	X	X
TICS-m*	X		X	X

COWAT*	X	X	X
TMT*	X	X	X
BDI*	X	X	X

---

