#### **Safety analysis:**

Adverse events occurring in the intraoperative period, immediate postoperative period and up to 4-8 weeks after the procedure will be recorded. We will collect specific adverse events that might be related to TXA treatment, including incidence of TTE, impaired renal function (plasma creatinine increase >20% of baseline level), and neurological complications, such as seizures and vision abnormalities. Adverse events apparently unrelated to use of the drug will also be recorded. The plasma creatinine will be obtained on POD1 and preoperatively. Severe adverse events are DVT and PE.

Sections including description of the anesthesia technique, transfusion requirements and blood loss, and venous thromboembolism prophylaxis are described in the Appendix. A comparison of the frequency and severity of adverse events occurring up to the 4-8-week follow-up period will be analyzed. Any SAE will be reported to the DSMB as they occur.

**Stopping rules or safety triggers for the study:** impairment in renal function and thromboembolic events will trigger a meeting of the DSMB to discuss the events and decide on the continuation of the trial. The study will automatically be placed on hold until the investigators and the DSMB can conduct a review of events. All AEs will be collected, recorded, and analyzed. Safety oversight for this study will be provided by both the DSMB and an independent Medical Safety Monitor. If the rate of thromboembolic events or impaired renal function crosses the literature threshold or the control group with 95% probability, the study will stop.

**Postoperative drain management:** The Hemovac drain is removed when the 8h output is <50 cc. The output is recorded for every 8 hour and charted.

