## Outcome assessment:

### 1) hemorrhage assessment:

- intraoperative [blood loss](#),
- [Total blood loss \(Calculated\)](#) and [Hidden Blood loss \(Calculated\)](#)
- [postoperative](#) drainage amount (per 8 h shift),
- days of drain in place, HGB level (before surgery and 1, 24h, 48 and 72 hours after surgery),
- [hematocrit](#) (HCT; same),
- [prothrombin time](#) (PT), PPT before,
- number of blood transfusions

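### Hidden blood loss subtracts drainage up to drain removal from a haematocrit-based total that ends at an unnamed blood draw, so it reads too low whenever the drain outlasts that draw

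*Protocol*

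**What the plan says.** The definitions are in the Protocol section Calculations and measurement of blood loss.

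- Visible loss: "Visible blood loss = intraoperative blood loss + postoperative drainage amount". No end time is set for the drainage.
- Hidden loss: "Hidden blood loss = total blood loss before and after surgery – visible blood loss".
- Total loss: "preoperative blood volume × (HCT difference before and after surgery/mean HCT before and after surgery". The section does not say which postoperative HCT enters.

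The timing comes from other sections.

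- Drain removal (Protocol, Safety analysis, drain management paragraph): "The Hemovac drain is removed when the 8h output is <50 cc", with no maximum duration. Also: "The output is recorded for every 8 hour and charted".
- Blood sampling (Protocol, Outcome assessment, hemorrhage assessment): "HGB level (before surgery and 1, 24h, 48 and 72 hours after surgery", with the same times for HCT. The schedule table after the exclusion criteria has an entry "Intraop 1h postop (PACU) POD1,2,3". Its row label is not legible in the text available, but the entry fits a last draw at about 72 h.
- Hypothesis (Protocol, Primary Hypothesis): "TXA reduces intraoperative and postoperative (up to 7 days) blood loss and transfusion requirements".

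The Primary endpoints section attaches 7 days to transfusion only and gives no window for blood loss. Hidden loss is listed under Outcome assessment. It is named neither among the primary endpoints nor in the primary analysis. The SAP defines none of these variables.

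**The concern.** A difference between two quantities has a clear meaning only if both cover the same period. Here the first term ends at a blood draw and the second at drain removal, and nothing ties one to the other. Drainage collected after the draw is subtracted from a total that cannot include it.

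The end of the drainage period is also set by the amount of bleeding. A patient who drains less is measured for a shorter time. The Protocol asks, as an exploratory objective, whether TXA changes drain duration. If it does, the arms are observed over different periods, both for drainage and for the drainage term inside hidden loss.

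Finally, the hypothesis extends blood loss to 7 days, while the HCT values needed for a calculated loss have stated times only up to 72 h.

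**Working it through.** The documents give no figure for hidden loss, so there is none to reproduce. The check applies the Protocol's own formula and drain rule.

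**1. Minimum drainage after the draw.** Under the removal rule, every 8-hour period before the last has at least 50 mL. The last has less than 50 mL, because that is what triggers removal, so it guarantees nothing. Assume that shifts line up with the draw and that the drain comes out at the end of the first period below 50 mL.

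- Drain kept 24 h past the draw: 24/8 = 3 periods, minimum (3 − 1) × 50 = 100 mL.
- Drain kept 48 h past the draw: 48/8 = 6 periods, minimum (6 − 1) × 50 = 250 mL.

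These minimums hold for any draw time, for example a 48 h draw with the drain out at 72 h, or a 72 h draw with the drain out at 96 h.

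**2. Scale.** Assume a man of 1.70 m and 80 kg whose HCT falls from 42 to 34.

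- Blood volume = 0.3669 × 1.70³ + 0.0322 × 80 + 0.6041 = 1.803 + 2.576 + 0.604 = 4.98 L.
- Total loss = 4.98 × (42 − 34)/38 = 1.05 L.
- 100/1050 = about 10%; 250/1050 = about 24%.

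The total serves here only as a yardstick; it has no drainage term and carries no error from this source. As a share of hidden loss the shortfall would be larger whenever hidden loss is only part of the total, but the documents do not allow that share to be computed.

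**3. When there is no shortfall.** With the 72 h HCT and the drain out by 72 h, all drainage lies inside the HCT window and the excess is 0 mL. A drain still in after 72 h needs nine consecutive outputs of at least 50 mL, that is at least 9 × 50 = 450 mL. The documents do not say how often that happens. With a 24 h or 48 h draw, no such long drain is needed.

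**4. Comparison between arms.** Assume 75 mL per period and 25 mL in the last.

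| HCT draw | Drain out, placebo | Drain out, TXA | Hidden loss too low, placebo | Hidden loss too low, TXA |
|---|---|---|---|---|
| 48 h | 72 h | 48 h | 2 × 75 + 25 = 175 mL | 0 mL |
| 24 h | 48 h | 48 h | 175 mL | 175 mL |
| 72 h | 72 h | 48 h | 0 mL | 0 mL |

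The arms differ only in the first row, where drainage continues past the draw and differs by arm. There placebo hidden loss is understated, which works against showing a TXA benefit on this outcome.

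**5. Seven days.** 7 × 24 = 168 h, and 168 − 72 = 96 h without an HCT at a stated time.

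**The case against.** The strongest reply is that this is a missing detail in a derived variable that is not a named primary endpoint. If the team uses the 72 h HCT, most or all drains may be out by then and nothing goes wrong. The calculated total does not use drain volume, and one removal rule applies to both blinded arms. All of this is correct and limits the point. It does not remove it: the Protocol does not say that the 72 h value is used, and even at 72 h the written rule subtracts later drainage. Naming the HCT time alone would not cure that.

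A reader might infer more than the documents support:

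- *The two terms always cover different periods.* They do not when the 72 h HCT is used and the drain is out by then.
- *The arms are biased differently.* This needs drainage beyond the draw and a difference in late drainage between arms. The effect of TXA on drain time is an open exploratory question.
- *Each 24 h past the draw costs at least 3 × 50 = 150 mL.* This ignores that the last period is below 50 mL.
- *Total blood loss is corrupted, or the components do not add up.* Hidden loss is defined as total minus visible loss, so they add exactly, and the calculated total is untouched.
- *No blood-loss data exist for days 4 to 7.* The schedule marks blood loss, drain output and CBC during hospitalization without a day limit, and drainage is charted until removal. Only the HCT-based quantities lack an HCT at a stated time after 72 h.

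**Conclusion.** The point holds in limited form. As written, hidden loss is understated for every patient whose drain outlasts the HCT draw used: by at least 100 mL at 24 h past the draw and at least 250 mL at 48 h. These minimums rest on the removal rule being followed and on shifts aligned with the draw; the 10% and 24% rest on the assumed patient. How many patients are affected cannot be determined, because neither the HCT time nor the expected drain duration is given.

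Bias between arms is possible but not established. If TXA shortens drainage, it runs against TXA on hidden loss. Separately, drainage to removal is observed over a period that the outcome itself sets. This matters if the primary endpoint of postoperative blood loss is taken from the drain, which the Protocol leaves open. A 7-day claim for HCT-based total or hidden loss has no support from HCT draws with stated times.

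**What to change.** - In Calculations and measurement of blood loss, and in the SAP, name one postoperative HCT time for the formula. Sum drainage only to that time from the charted 8-hour outputs, with a rule for a draw that falls within a shift. The excess is then 0 mL by construction at 24, 48 or 72 h.
- Optionally, report drainage to the same fixed time beside drainage to removal, so that both arms are also compared over one common period.
- Reword the Primary Hypothesis so that calculated blood loss ends at the chosen HCT time and 7 days applies to transfusion, as the Primary endpoints section already has it.

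The cost is wording in two documents and a re-sum of outputs that the Protocol already has charted. Drain care does not change and no new measurement is needed. The downside is a shorter claimed window for calculated blood loss, 72 h at most instead of 7 days.

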**Primary endpoints:**

1. The amount of RBC transfusion intraoperatively
2. The amount of RBC transfusion up to 7 days postoperatively
3. Measurement of intraoperative blood loss, postoperative blood loss, and total blood loss.

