#### **Analysis of Primary End Point:**

The primary endpoint is the mean difference in total blood loss, intraoperative blood loss and postoperative blood loss. An ANOVA will be used to compare between the 2 groups. A type I error rate of 0.05 will be utilized. An exploratory GLM ANOVA will be used to test for interaction for the subgroups with number of level fused, BMI and duration of surgery.

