Cover Page for Statistical Analysis Plan

Sponsor-Investigator:	[name]
NCT Number:	NCT04272606
Unique Protocol ID:	201912099
Official Title:	Prospective, Randomized, Double Blind Study on the Effects of Tranexamic Acid on Intraoperative Blood Loss During Lumbar Spinal Fusion And Instrumentation
Date of Document:	05 December 2023

Statistical Analysis

All analyses will be conducted using R statistical software (version 4.3.1). Continuous variables will be summarized using medians and interquartile ranges and comparisons between groups will be done made using Wilcoxon rank sum or Kruskal-Wallis tests. Pairwise analyses within a group will be made using the Wilcoxon signed rank test. Categorical variables will be summarized using counts and percentages, and comparisons between groups will be performed using Pearson χ^2 test or Fisher exact test. Kendall's tau (τ) will be used as a non-parametric test of association between variables. For all analyses, the threshold for significance will be <0.05 without adjustment for multiple comparisons. Variables will be compared between groups by calculating standardized mean differences.

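### Calculated total blood loss, a primary endpoint, has no term for transfused red cells, so it reads too low in transfused patients and pulls the effect toward zero if TXA reduces transfusion

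*Protocol*

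**What the plan says.** In the protocol section on calculations and measurement of blood loss, total loss is obtained only from the fall in HCT: "Total blood loss before and after surgery = preoperative blood volume × (HCT difference before and after surgery/mean HCT before and after surgery"). Hidden loss is then a remainder: "Hidden blood loss = total blood loss before and after surgery – visible blood loss". Visible loss is a separate quantity, the sum of intraoperative loss and drainage.

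Total loss is a primary endpoint in two places. The list of primary endpoints has "Measurement of intraoperative blood loss, postoperative blood loss, and total blood loss", and the primary analysis section states: "The primary endpoint is the mean difference in total blood loss, intraoperative blood loss and postoperative blood loss". The hemorrhage assessment list labels both total and hidden loss as calculated.

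That list schedules "HGB level (before surgery and 1, 24h, 48 and 72 hours after surgery"), with HCT at the same times. No section says which postoperative value enters the formula. Transfusions are recorded but not used in it. The primary objective adjusts blood loss for weight, duration and levels fused, not for transfusion. The SAP mentions neither the formula nor a correction.

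**The concern.** A unit of red cells given before the HCT draw raises the postoperative HCT. That shrinks the numerator of the formula (the HCT difference) and enlarges the denominator (the mean HCT), so calculated loss falls although bleeding is unchanged. An intraoperative unit precedes all four draws. Units given after the chosen draw have no effect.

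The primary hypothesis is that "TXA reduces intraoperative and postoperative (up to 7 days) blood loss and transfusion requirements". If the transfusion part is true, placebo patients receive more red cells, their loss is under-counted more, and the estimated reduction in total blood loss is biased toward zero. One primary endpoint then distorts another. Hidden loss inherits the error and can become negative, which is physically impossible.

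**Working it through.** The plan gives no worked figure for this formula, so there is none to reproduce. The check applies the formula to the same bleeding with and without transfusion.

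**One patient.** Assumed: blood volume V = 5.0 L, HCT 0.40 falling to 0.21, 180 mL (0.18 L) red cells per unit, volume restored. The correction adds red-cell volume ÷ mean HCT.

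| Units before the draw | Postop HCT | Mean HCT | Formula as written | With added term |
|---|---|---|---|---|
| 0 | 0.21 | 0.305 | 5.0 × 0.190 / 0.305 = 3.11 L | 3.11 L |
| 1 | 0.21 + 0.18/5.0 = 0.246 | 0.323 | 5.0 × 0.154 / 0.323 = 2.38 L | 2.38 + 0.18/0.323 = 2.94 L |
| 2 | 0.21 + 0.36/5.0 = 0.282 | 0.341 | 5.0 × 0.118 / 0.341 = 1.73 L | 1.73 + 0.36/0.341 = 2.79 L |

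If 75% of the untransfused total is visible (assumed; 0.75 × 3.11 = 2.33 L), hidden loss is 0.78 L, 0.05 L and −0.60 L with zero, one and two units.

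**Between-arm difference, by simulation.**

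- True mean difference 682 mL, from the 681.81 mL in the protocol's sample size section.
- Lognormal loss, same SD in both arms, taken in 50 mL isovolemic steps (each multiplies HCT by exp(−d/V)). One unit is given whenever HCT falls below a trigger.
- All units precede the HCT used. Blood volume has mean 5.0 L and SD 0.7 L; 40,000 patients per arm.
- 16 scenarios: placebo mean loss 1500 or 1900 mL; SD 700 or 940 mL; 150 or 200 mL red cells per unit; mean preoperative HCT 0.38 or 0.42. The protocol gives no SD. The 940 mL is what 40 per arm, 90% power and two-sided 0.05 imply: 681.81 × √20 / (1.960 + 1.282) ≈ 941 mL.
- Triggers start at 0.21 and 0.24, about Hb 7 and 8 if HCT is taken as three times Hb. They extend to 0.27 and 0.30 because the indication for transfusion also lists symptoms such as "A decrease in blood pressure to <100 mmHg systolic", most with no Hb limit beside them.

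The table shows the share of the difference lost relative to the same formula without transfusion, as range (middle value). The median is included because the SAP states: "Continuous variables will be summarized using medians and interquartile ranges".

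| HCT trigger | Placebo patients transfused | Mean difference lost | Median difference lost |
|---|---|---|---|
| 0.21 | 3–16% | 2–15% (7%) | 0–10% (2%) |
| 0.24 | 8–31% | 6–33% (17%) | 2–30% (11%) |
| 0.27 | 19–57% | 16–58% (34%) | 10–54% (31%) |
| 0.30 | 36–81% | 34–82% (59%) | 29–80% (54%) |

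A repeat with a preoperative HCT SD of 0.035 gave the same mean-difference ranges to within about a point. Scaling the TXA-arm SD down with its mean raises them to 4–24%, 10–44%, 23–69% and 43–89%.

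**Null check.** With no TXA effect (200,000 per arm), the difference is 1–2 mL at every trigger, so no spurious effect is created.

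**The case against.** **Little effect on the planned test at low triggers.** The SAP compares groups by Wilcoxon rank sum. Across the grid, the mid-range probability that a placebo patient's total exceeds a TXA patient's moves only from 0.790 to 0.789 at HCT 0.21 and from 0.787 to 0.784 at 0.24. A visible drop appears at 0.27 (0.790 to 0.763) and 0.30 (0.790 to 0.695). This stands. At low triggers the harm is to the estimate rather than the test, and no power loss is claimed here.

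**The high triggers rest on one reading.** The symptom list may be one sentence whose closing limit, Hb 7.0 to 8.0, governs every item. Then only the 0.21 and 0.24 rows apply. The text can be read either way, so the rows are kept separate.

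**Worst-case timing.** The ranges assume all units precede the HCT used. That is certain only for intraoperative units, so the bias is smaller if some units come later.

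**Total may mean intraoperative plus postoperative loss.** The endpoint lists could be read as a sum. But the protocol already calls that sum visible loss and labels total as calculated, so the formula is the better reading. If a sum was intended, the text should say so, and calculated total and hidden loss remain listed outcomes.

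**The bias is conservative and other endpoints are sound.** Both are true. The primary aim and the official title centre on intraoperative loss, which is unaffected. That limits the importance but does not make a biased primary estimate acceptable.

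**Conclusion.** The concern holds. As written, the formula understates total and hidden blood loss in any patient transfused before the HCT used, and it biases the TXA effect on total loss toward zero under the trial's own hypothesis. The direction follows from the algebra. The size depends on the transfusion rate, the red cells per unit and the HCT time, none of which the documents fix. Mid-range, 7–17% of the mean difference is lost at triggers of 0.21 to 0.24, and 34–59% at 0.27 to 0.30. This should be fixed, but it does not undermine the trial: it adds no false-positive risk and leaves weighed intraoperative loss, drain output and RBC transfusion untouched.

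**What to change.** Write in both the protocol's calculation section and the SAP:

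> Total blood loss = preoperative blood volume × (HCT difference / mean HCT) + (red-cell volume transfused up to that HCT) / mean HCT, where red-cell volume = units × [stated unit volume] × [stated unit HCT]. The postoperative HCT is the one scheduled at [one named time] for all patients. Hidden blood loss = this total minus visible loss.

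Describe this as an approximate correction. Add a sensitivity analysis over the assumed red-cell content per unit (for example 150–200 mL), and report the uncorrected total alongside.

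The cost is wording and one derived variable. HCT and transfused amounts are already collected, but each unit must be placed before or after the chosen draw.

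The correction is not exact. In the worked patient it recovers 2.94 L and 2.79 L of 3.11 L. In the simulation it leaves 0–5% of the mean difference lost when unit content is known. If 180 mL is assumed but the truth is 150 or 200 mL, the error runs from 11% over to 12% under at trigger 0.30, and from 0% to 4% under at 0.21. The corrected version can therefore overstate benefit, which the current one cannot. That is the reason to report both.

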## Outcome assessment:

### 1) hemorrhage assessment:

- intraoperative [blood loss](#),
- [Total blood loss \(Calculated\)](#) and [Hidden Blood loss \(Calculated\)](#)
- [postoperative](#) drainage amount (per 8 h shift),
- days of drain in place, HGB level (before surgery and 1, 24h, 48 and 72 hours after surgery),
- [hematocrit](#) (HCT; same),
- [prothrombin time](#) (PT), PPT before,
- number of blood transfusions

